## **6.0 Number of Subjects**

- A total of eight subjects will be recruited to participate in this study.

## **7.0 Setting**

- All activities will be conducted in a Laboratory located on the Medical University of South Carolina campus.

## **8.0 Recruitment Methods**

- Study participants will be recruited from our Registry for Stroke Recovery that has information of 680 stroke survivors stroke who have agreed to be contacted for research (RESTORE, approved MUSC IRB PRO# 37803, [name] PI). In addition to the registry, advertisement via internet (e.g. South Carolina Research Studies Directory) will be used.

## **9.0 Consent Process**

- The consent process will take place in a private room when the potential participant comes to the laboratory on a scheduled time agreed upon between the study personnel and the participant. The content of the consent will be verbally explained to the participant and the participant will be asked to raise any questions and concerns. If the person requests a waiting period, then one will be given. If the person desires to consent immediately, then the person will provide consent immediately.

## **10.0 Study Design / Methods**

- Study design: A single cohort study. Describe what subjects will do. Subjects will receive 6-week standardized task-practice therapy with TheraBracelet on their affected wrist (2 hr/d, 3d/wk, 18-session). Clinical assessments will be performed at baseline, after each week of therapy, and at 1-month follow-up. Change in brain FC during rest before vs. after the first therapy session will be assessed using fMRI and EEG independently.
- Schedule: Participation in the study will last approximately 10 weeks. Participants will visit the laboratory 3 times a week for 6 weeks (18 sessions) to receive treatment. Additionally, participants will visit the laboratory for 3 assessment visits (before and after the treatment intervention and at one-month follow-up).

- MRI: MRI assessments will be performed two times, before and after the initial therapy session. The first scan will be for 1 hour. The second scan will be for 30 minutes. Subjects will rest on a scanner bed and either rest or press buttons with the fingers for the first scan while their resting or task fMRI is obtained. In addition to fMRI, structural MRI scan will be obtained for the individual participant's brain anatomy.
- EEG: For the EEG assessment, participants will wear an EEG cap on their head. Gel will be applied to individual EEG electrodes with a blunt syringe that does not penetrate the skin (taking approximately 30 min for this preparation). During the assessment, the participant will rest comfortably in a chair and either rest or grip with the fingers. The EEG assessment will take approximately 0.5 hour to complete, in addition to the 30 min prep time.
- Clinical Assessment: The clinical assessment will include measurement of the hand function scores using the Wolf Motor Function Test, Box and Block Test, and Action Research Arm Test, and completion of a patient-centered outcomes questionnaire on self-reported abilities for activities of daily living using Stroke Impact Scale hand subscale. For the hand function scores, participants will move the affected hand, grasp objects, and perform prescribed tasks (e.g. lifting the object off the table, releasing the object into a bin) as quickly as possible. These tests will be videotaped for quality control purposes. These tests will be scored by a therapist. For the patient-centered outcomes questionnaire, Stroke Impact Scale hand subscale will be administered through pen-and-paper administration. The questionnaire is to assess if the hand functional improvement translates to self-reported abilities for activities of daily living. Additionally, acute responsiveness to vibration will be assessed for all subjects by repeating measurement of the sensory and motor scores of the Monofilament Test and Box and Block Test while the device delivers vibration. The clinical assessment will take approximately 1 hour to complete.
- Protection against risk: For fatigue, frequent and sufficient breaks will be provided to participants. Fatigue and pain will be monitored using a visual analog rating scale administered immediately before and after each therapy or assessment session. Depending on the change in the fatigue/pain rating, the therapy tasks to be practiced will be graded in terms of its difficulty to reduce excessive fatigue and pain (i.e. If the participant experiences finger joint pain, s/he may try gross grasping as opposed to finger individuation. If the participant experiences shoulder pain, s/he may lower the reaching target or object location to reduce shoulder flexion requirements). The comfort will be maximized by using cushions, adjusting table or chair heights, adjusting the back rest, using a foot rest, etc.

For potential skin irritation due to wearing the wristband, the wristband tightness may be adjusted or a new wristband may be tried to maximize participant comfort. For the EEG assessment, the gel used for the electrodes can be washed off with shampoo. The participant will be advised to bring a hat to wear for the way home.

For the MRI, all participant receiving MRI are required to complete a screening questionnaire to ensure that the person does not have any loose metal objects such as earrings or nose rings or a piece of metal in the body such as a fragment in the eye, aneurysm clips, ear implants, spinal nerve stimulators, a pacemaker, or an implant electrical device. Persons with potential for pregnancy will be excluded. Each person

will be screened before each MRI assessment. To prevent hearing loss, the participant will be asked to wear earplugs and headphones for MRI.

Potential risks that may be associated with use of wrist vibration (wrist skin irritation, increased upper limb pain, increased spasticity, weakened grip strength, worsening of hand sensation, and worsening of hand dexterity) will be systematically assessed at all times (for evaluation time points including after each week of continuous therapy and 1-month follow-up, as compared to baseline) as safety data. Negative changes in these safety measures will be communicated to the participant immediately and be explained. In addition, any other adverse events regardless of whether it is related to the device or not will be explicitly asked and recorded at all evaluation time points as well as any time they occur. All of these safety data and adverse event information, in addition to the daily safety screening and fatigue/pain monitoring data, will be reported to the DSMB, IRB, clinicaltrials.gov, and in publications.

Participants will be notified if we learn anything that might make them change their mind about participating in the study. Participants will be informed that they can drop out of the study at any time without penalty.

## 11.0 Data Management

- Analysis: we will test if the clinical outcome is associated with change in FC after one session (representing motor memory consolidation activity) by constructing a linear regression model.
- Sample size justification: This is a pilot study with n=8. We target to complete data collection for 4 subjects.
- Confidentiality: All data except for the consent forms and HIPPA forms will be de-identified at the time of data recording. All electronic data will be stored in a password-protected research server that is accessible to study personnel only. The server is backed up every day and maintained 24/7 by IT specialists. All paper data with personally identifiable information including the consent forms and HIPPA forms will be stored in a key-locked cabinet in a key-locked room that is accessible to study personnel only. Other paper data without personally identifiable information including testing sheets documenting testing sequences and notes will also be stored in a cabinet in a key-locked room that is accessible to study personnel only.
- Data sharing: Only de-identified coded data will be reported and/or shared with the public and other investigators in publications, in ClinicalTrials.gov, or via network storage.

## 12.0 Provisions to Monitor the Data to Ensure the Safety of Subjects

The proposed research is a single-site pilot proof-of-concept clinical trial that involves an intervention of standardized task-practice therapy combined with an investigational device. A Data Safety Monitoring Board (DSMB) will be used. The primary purpose of the DSMB is to ensure the safety of participants and the validity and integrity of data collected during the study. The overall framework involves review of the enrollment/retention and safety and adverse event data by the DSMB during the proposed research.

- DSMB composition: The DSMB will be composed of (1) a board certified stroke neurologist who is also a stroke recovery researcher, is a Director of the Post-Stroke

Spasticity Clinic, and is experienced in care of chronic stroke survivors and their recovery; (2) a registered and licensed occupational therapist who is also a quantitative researcher in outcomes measurement and research design; and (3) a biostatistician with expertise in design and analysis of clinical trials. The three individuals bring substantial expertise adequate to monitor data and safety for this stroke recovery intervention clinical trial.

- **DSMB responsibilities:** The responsibilities of the DSMB are as follows. Prior to any enrollment, the DSMB will review the study design, protocol, recruitment/enrollment plan, statistical analysis plan, and data and safety monitoring plan, and document the agreement or recommendation. After the enrollment begins, the DSMB will convene to review the enrollment data, and the safety and adverse event data (see below for detailed data description) at the end of the study, unless an adverse event occurs in which case the PI will inform the DSMB immediately and the DSMB will review the incidence at that time. The DSMB will review the aggregated summary data as well as the individual participants' data (de-identified). The DSMB will provide recommendations for any safety concerns. The DSMB may recommend stopping the study early if the intervention has safety concerns. The DSMB will review the results and document their reviews in writing. In summary, the stopping rules are if the study has unanticipated safety concerns that warrant stopping. The DSMB will also provide a report to the IRB to summarize oversight activities, recommendations, and any concerns regarding participant safety.
- **Data to be reviewed by DSMB:** Two types of data will be reviewed by the DSMB.
  1. **Enrollment/retention data:** Enrollments, progression of the enrollees' participation in the study, and any discontinuation of participation in the study with or without adverse events will be reviewed.
  2. **Safety and adverse event data:** At every visit, participants' safety will be monitored in the following procedure. For daily safety screening, each participant's blood pressure and heart rate will be assessed upon their arrival to the laboratory. Abnormal level, compared to their baseline, will trigger consulting with the study clinician, rescheduling the visit, or seeking medical attention by calling the participant's doctor and/or sending the participant to the emergency room especially if severe headache and blurry vision are experienced. This daily screening will be documented.

For safety monitoring during each visit, we will monitor pain and fatigue on a visual analog scale prior to beginning and immediately after each therapy or assessment session. This information, in comparison to baseline, will be used to grade task activity to prevent excessive pain or fatigue in patients during therapy (i.e. If the participant experiences finger joint pain, s/he may practice tasks involving gross grasping as opposed to finger individuation. If the participant experiences shoulder pain, s/he may lower the reaching target or object location to reduce shoulder flexion requirements). During assessment, comfort will be maximized using cushions or adjusting a foot rest, table height, back rest, etc. Excessive pain or fatigue that cannot be modified will lead to termination in the participation in this research study.

Safety of using the TheraBracelet device will be assessed at each evaluation time point. Effects of using TheraBracelet on hand function scores (the Wolf Motor

Function, Box and Block, and Action Research Arm scores) are assessed after each week of therapy and at 1-month follow-up, compared to baseline. In addition to the hand function scores, broad aspects of safety will be systematically assessed at all evaluation time points for all participants as part of clinical assessments. These safety data will include any wrist skin irritation (verbal report and/or visual examination), increased upper limb pain level (on a visual analog pain rating scale from 1 to 10), increased spasticity (on the Modified Ashworth Scale), weakened grip strength (using Jamar grip dynamometer), and worsening of hand sensation (using the Semmes-Weinstein Monofilament Test score), compared to baseline. Decline will be considered as an adverse event if a reasonable criterion is met: if the participant exhibits wrist skin irritation that did not exist prior to the intervention, if the pain level increases by more than 2 points, if the Modified Ashworth Scale increases by more than 1 level (equivalent to the effect size of botulinum toxin A), if grip strength declines by more than 20% from the baseline which is approximately 2 standard deviation of the population data, if the Monofilament Test declines by one category (e.g. “normal” to “diminished light touch”) with a change of more than two points, and/or if the hand function scores decline by more than the larger of the minimum detectable change and the minimal clinically meaningful difference reported in literature. Negative changes in these measures will be communicated to the participant immediately and be explained. A potential need for medical attention will be discussed.

Any adverse events, regardless of whether it is related to the device or not, will also be explicitly asked and recorded at all evaluation time points. These safety assessments will add additional 10 minutes to the clinical assessment at each evaluation time point.

All daily safety screening, pain/fatigue, and safety/adverse event information will be recorded de-identified (coded). Coded paper documents will be stored in a locked cabinet in a locked office, and coded electronic data will be stored in a password-protected research server. They will be accessible to only study personnel. All daily screening, pain/fatigue, and safety/adverse event data will be tabulated for each time point. All adverse events will be summarized in terms of frequency, severity, and relatedness to the study intervention using the Medical Dictionary for Regulatory Activities code (MedDRA).

Reporting of safety data: All adverse events will be reported to the IRB as they occur. All enrollment/retention data, and safety and adverse event data will be reported to the DSMB during the review. The DSMB will review the data and submit a report to the IRB. Summative safety data will be reported to ClinicalTrials.gov, and in publications. As such, we will register this study in ClinicalTrials.gov as soon as the study commences and report results including all adverse events as soon as the study is completed following the guidelines. To protect participants' confidentiality, personally identifiable information will not be used for reporting. Only de-identified or aggregated data will be used for reporting.

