## 13.0 Withdrawal of Subjects (if applicable)

- Subjects who do not show up on scheduled visits may be withdrawn by the investigator.

- For those who voluntarily withdraw from the research, their data collected up to that point may be used by the investigator.

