## 14.0 Risks to Subjects

- There is a slight risk for loss of confidentiality although researchers will take appropriate steps to protect any information collected about the participants. There is a minor risk of physical and mental fatigue from engaging in the study activity. There is a minor risk of skin irritation from wearing the wristband. There is a minor risk of discomfort in moving the arm/hand while wearing a device on the wrist, although the TheraBracelet device weighs only 40 g.
- For the EEG assessment, there is a minor risk of discomfort in wearing a head cap attached with a bundle of wires. Also, the gel used for the electrodes will get hair messy. For the MRI, there is a serious risk that MRI could move iron-containing objects in the MRI room, which could in the process possibly harm the person. The 3T MRI scanner is unsafe for pregnancy. There is discomfort by claustrophobia and by the loud banging noise. Temporary hearing loss has been reported from the loud noise from the MRI machine. The person may also feel uncomfortable as s/he will be asked not to swallow for a while.
- Potential risks that might be associated with use of wrist vibration for a prolonged time include wrist skin irritation, increased upper limb pain, increased spasticity, weakness, and worsening of hand sensation or dexterity. These risks are expected to be rare because the intensity of vibration used in TheraBracelet is subliminal while we are exposed to higher-intensity, suprathreshold vibration daily (e.g. from a phone, car). Currently there is no vibration exposure guideline for this small level of vibration, as the U.S. Occupational Safety and Health Administration provides vibration exposure guidelines only for high-intensity vibration such as jackhammers and hand-held powered drills. Currently there are no known side effects using this small imperceptible (unfelt) level of vibration used in the proposed study. TheraBracelet has been used during hand task practice therapy in chronic stroke survivors for a total of 12 hours without any adverse events including no skin irritation in our pilot study. In addition, the investigators have used TheraBracelet vibration for 12 hours/day every day for 1 month continuously with no safety issues, including no skin irritation. Nonetheless, safety of using TheraBracelet will be systematically monitored.

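### Unmanageable pain or fatigue ends study participation, not just treatment, and no visible section provides safety follow-up after that stop

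*Combined protocol and SAP*

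**What the plan says.** Section 12.0 (safety and adverse event data) has pain and fatigue rated on a visual analog scale before and after every therapy or assessment session, and the tasks regraded accordingly. Where regrading and comfort measures fail, "Excessive pain or fatigue that cannot be modified will lead to termination in the participation in this research study".

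The same section plans safety follow-up through scheduled visits: "broad aspects of safety will be systematically assessed at all evaluation time points for all participants as part of clinical assessments". Under Sections 10.0 and 12.0 those time points fall after each week of therapy and at 1 month. Reporting is by time point: "All daily screening, pain/fatigue, and safety/adverse event data will be tabulated for each time point".

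On oversight, the Data Safety Monitoring Board (DSMB) normally meets once the study has finished. An adverse event brings its review forward: "in which case the PI will inform the DSMB immediately and the DSMB will review the incidence at that time". It also reviews every discontinuation. Adverse events go to the IRB as they occur.

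Section 13.0 deals with missed visits and voluntary withdrawal. For voluntary withdrawal it says only that "their data collected up to that point may be used by the investigator". Section 14.0 says the potential risks of "use of wrist vibration for a prolonged time include wrist skin irritation, increased upper limb pain, increased spasticity", along with weakness and worse sensation or dexterity. Section 11.0 gives n=8 and adds: "We target to complete data collection for 4 subjects".

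**The concern.** Stopping treatment and stopping observation are separate decisions, and this sentence makes both at once. Participants leave the safety schedule because of a safety outcome, so the people missing from later tables are those whose pain or fatigue was worst.

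For pain this touches one of the plan's own listed device risks. Section 12.0 gives it a formal adverse event threshold, an increase of more than 2 points. Treatment exposure is also substantial. Section 10.0 plans 18 sessions of 2 hours, which is 36 hours (18 to 36 under the 1 to 2 hours of Section 3.0). A reader of the results would learn that someone stopped for pain, but not whether the pain settled once treatment ended.

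**Working it through.** The plan states no figure on this point, so the main check is of the text. The arithmetic only gives scale.

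**1. What is captured, and when**

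| Provision | Captures | After the stop? |
|---|---|---|
| Ratings around each session (12.0) | Onset, including the session that triggers the stop | No; no further sessions |
| Adverse events recorded at evaluations and whenever they occur (10.0) | Occurrence | No later contact specified |
| Immediate notice to DSMB; reports to IRB (12.0) | Occurrence | No later assessment specified |
| DSMB review of discontinuations (12.0) | The fact of stopping | Later course not mentioned |
| Talk about possible medical attention (12.0) | Advice to the participant | Not data collection |
| Safety checks for all participants (12.0) | Status at each evaluation | Tied to clinical assessments that a terminated person no longer attends |
| Withdrawal rules (13.0) | No-shows and voluntary withdrawal | This rule not addressed; earlier data only for voluntary exits |

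No row provides an assessment after termination.

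**2. Time left unobserved**

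Therapy runs 6 weeks and participation lasts about 10 weeks (Section 10.0). For a stop at the end of week w, the week-6 assessment is 6 − w weeks later and the 1-month visit about 10 − w weeks later. For w = 1 to 5 that is 5 to 1 weeks and 9 to 5 weeks.

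**3. Effect on a 1-month table**

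Assumptions: one person is stopped, nobody else has lasting harm, and the table covers only those assessed. The one-sided 95% upper bound is 1 − 0.05^(1/n) for 0/n, and the Clopper-Pearson limit, the 0.95 quantile of Beta(2, n − 1), for 1/n.

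| Scenario | Not followed | Followed, cleared | Followed, lasted |
|---|---|---|---|
| 4 completers + 1 stopped | 0/4, bound 53% | 0/5, bound 45% | 1/5 = 20%, bound 66% |
| 7 completers + 1 stopped | 0/7, bound 35% | 0/8, bound 31% | 1/8 = 12.5%, bound 47% |

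Example: 1 − 0.05^(1/4) = 1 − 0.473 = 0.527. The first scenario accounts for 5 of the 8 recruits. The other three would have left for other reasons, which this point does not address.

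**4. Chance that the rule is used at all**

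No rate is given. With an assumed per-person risk p, the chance of at least one such stop among 8 is 1 − (1 − p)^8:
- p = 5%: 34%
- p = 10%: 57%
- p = 20%: 83%

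**The case against.** The strongest reply is that the rule is protective and little is lost. The sentence follows directly on comfort measures during assessment, so it also covers people who cannot tolerate being assessed. The clinical assessment takes about an hour and includes timed hand tasks. The vibration is subthreshold and the device was determined to be non-significant risk (Section 3.0). The DSMB sees individual data and makes recommendations, so it could ask for follow-up. Safety is not among the stated aims. All of this stands and keeps the point small. It does not supply the missing assessment, and ending treatment alone would protect the participant equally well if later checks are voluntary and brief.

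A second reply concerns what is visible. Consent pages were removed before review and may contain follow-up terms, and informal clinical contact may happen. This also stands. The claim can only be that no visible section provides follow-up. A reader might infer that these participants' later course would certainly go unseen, or that the DSMB could receive nothing further. The documents do not say so.

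A third reply is that the device-safety argument covers pain but not fatigue. That is correct: fatigue is not on the list of vibration risks, and Section 14.0 attributes it to taking part in study activity. Following fatigue is reasonable care, but it is not evidence about a listed device risk.

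**Conclusion.** The point holds in a limited form. As written, the rule removes people from the planned safety assessments because of a safety outcome, and no visible section provides for recording whether their problem resolved. The number affected is unknown and may be zero; the one-person tables are illustrations. With bounds between 31% and 66% in every scenario, follow-up would add almost no precision. Its value is knowing what happened to that individual.

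Three stronger readings are not supported.
- **Adverse events are hidden or undercounted.** Onset is recorded and reported, and the overall adverse event summary still counts an early stopper whose problem was recorded as an adverse event.
- **Participants with adverse events are generally dropped.** The rule does not reach skin, spasticity, grip, sensory or hand-function events, or pain that can be managed.
- **The main analysis is biased by this.** The hypothesis in Section 1.0 concerns motor gains after all sessions are completed, so safety follow-up of early stoppers leaves the regression as it is.

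Nor would follow-up show cause. Therapy and device stop together in a single cohort, so later improvement could not be credited to removing either one. This is a change worth considering, not a flaw that alters a planned conclusion.

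**What to change.** Replace the sentence in Section 12.0 with wording such as: *If pain or fatigue remains excessive despite modification, therapy and device use will end. With the participant's agreement, a safety check will be done at the stop and the scheduled week-6 and 1-month safety assessments will be kept, in person where tolerated, or by phone for pain, fatigue and adverse events.* State that these data enter the safety tables, and record the stop date, the reason and the sessions received. Add a matching consent sentence if none exists. Leave the regression on those who complete treatment.

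Cost: three contacts per early stopper (stop, week 6, 1 month). For time, Section 12.0 says: "These safety assessments will add additional 10 minutes to the clinical assessment at each evaluation time point". Taking 10 minutes per contact as an assumed minimum gives 3 × 10 = 30 minutes. In-person visits take longer because of the arrival blood pressure and heart rate check.

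Three contacts cannot date resolution closely. Weekly calls would do better but are optional. For a stop at the end of week 2 with a problem lasting to 1 month, calls in weeks 3, 4, 5, 7, 8 and 9 bring the total to 3 + 6 = 9 contacts, or 90 minutes on the same assumption.

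The downsides are some burden on people already in pain or fatigued, some refusals, and the fact that a phone call cannot measure grip, spasticity or sensation.

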### Inclusion Criteria

- Age = 18 or older
- At least 6 months post-stroke
- Moderate upper limb impairment with the ability to participate in hand task practices
- Fingertip touch sensory deficits (e.g., Monofilament>2.83, 2-point discrimination>5mm, sense of numbness, tingling)

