### Exclusion Criteria

- Complete upper limb deafferentation
- Rigidity (Modified Ashworth Scale=5)
- Botulinum toxin injection within 3 months prior to enrollment or during enrollment
- Brainstem stroke
- Comorbidity (peripheral neuropathy, orthopaedic conditions in the hand that limit ranges of motion, premorbid neurologic conditions, compromised skin integrity of the hand/wrist due to long-term use of blood thinners)
- Concurrent upper extremity rehabilitation therapy
- Language barrier or cognitive impairment that precludes following instructions or providing consent
- MRI incompatible.
- Screening: Eligibility will be determined based on the potential participant's verbal disclosure.
- Inclusion of Women and Minorities: We will include chronic stroke survivors of all genders and all racial and/or ethnic groups that are representative of the demographics of Americans who had a stroke. We will not exclude people based on sex/gender, racial or ethnic group. Specifically, according to data from the 2013 Behavioral Risk Factor Surveillance System, BRFSS (CDC), 2.7% of men and 2.7% of women  $\geq$  18 years of age had a history of stroke. Thus, approximately the same number of women and men will be recruited for this study. Also, according to the same data, 2.5% of non-Hispanic whites, 4.0% of non-Hispanic blacks, 1.3% of Asian/Pacific Islanders, 2.3% of Hispanics of any race, 4.6% of American Indian/Alaska Natives, and 4.6% of other races or multiracial people had a history of stroke. Thus, considering the stroke prevalence in each racial and ethnic group from the BRFSS together with the racial and

ethnic distribution of the American population from the 2010 U.S. Census, we will target enrollment of stroke survivors of all racial and ethnic groups accordingly.

- Exclusion of Children: We will recruit individuals who have had a stroke at least 6 months ago, who are 18 years old or older. Children under the age of 18 years will be excluded. The rationale for exclusion of children is that stroke predominantly occurs in adults, and stroke is very rare in children.

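### Wrist skin irritation may be recorded from verbal report alone in people selected for fingertip touch deficits, and no baseline skin inspection is required

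*Combined protocol and SAP*

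**What the plan says.** All places are in the combined protocol and SAP.

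- **How skin irritation is ascertained (section 12.0).** The safety data include "any wrist skin irritation (verbal report and/or visual examination". Either method alone satisfies this.
- **When it becomes an adverse event (section 12.0).** The criterion is "if the participant exhibits wrist skin irritation that did not exist prior to the intervention". It has no severity threshold and names no inspection.
- **Who is enrolled (section 5.0, Inclusion Criteria).** "Fingertip touch sensory deficits (e.g., Monofilament>2.83, 2-point discrimination>5mm, sense of numbness, tingling". The only upper limit on sensory loss, under Exclusion Criteria, is "Complete upper limb deafferentation".
- **Where the device is worn (section 10.0).** Participants receive "6-week standardized task-practice therapy with TheraBracelet on their affected wrist".
- **Standing of the risk.** Skin irritation is a named device risk in section 10.0 ("Potential risks that may be associated with use of wrist vibration (wrist skin irritation, increased upper limb pain, increased spasticity") and in section 14.0 ("use of wrist vibration for a prolonged time include wrist skin irritation").
- **Earlier experience (section 14.0).** The stroke pilot is reported as 12 hours of use in total with no adverse events and no skin irritation. Separately, "the investigators have used TheraBracelet vibration for 12 hours/day every day for 1 month continuously with no safety issues, including no skin irritation".

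**The concern.** The least demanding method that the plan permits relies partly on what the participant feels in a limb with a sensory deficit. If wrist sensation is reduced, irritation under the band may go unreported unless somebody happens to see it.

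Three things in the plan depend on its being noticed:

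- **The adverse event count.** Any new irritation qualifies, so the threshold is low and the count is sensitive to how hard staff look.
- **Early review.** Under section 12.0 the DSMB meets at the end of the study unless an adverse event brings it in sooner.
- **The comfort measure in section 10.0.** Adjusting or replacing the wristband can respond only to irritation that has been seen or reported.

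The safety results go to the DSMB, the IRB, the trial registry and publications. A report of no irritation is worth more if somebody looked.

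**Working it through.** The documents give no irritation rate and no sensitivity for verbal report, so there is no figure of the plan's own to reproduce. The check is a comparison of passages, followed by an illustration under stated assumptions.

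**1. Does another provision require inspection?**

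| Provision | What it covers | Requires looking at the skin? |
|---|---|---|
| Daily screening (12.0) | Blood pressure, heart rate | No |
| Monitoring at each session (12.0) | Pain and fatigue ratings by the participant | No |
| General adverse event enquiry (12.0) | Participant is asked | No |
| Skin item in the safety data (12.0) | Verbal report, inspection, or both | Optional |
| Adverse event criterion for skin (12.0) | New irritation against the pre-intervention state | No |
| Wristband adjustment (10.0) | Response to irritation | No |

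None closes the gap. In the same paragraph of section 12.0, spasticity, grip strength and hand sensation each have a named test.

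**2. Is there a baseline to compare with?** Section 12.0 compares safety measures with baseline. For skin, that baseline may also be verbal only. A judgement that irritation is new then has no required observation behind it.

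**3. How many evaluations are involved?** Baseline 1 + weekly 6 + one-month follow-up 1 = 8 per participant. Irritation caused by the device can arise only at the 7 after baseline. The baseline evaluation matters as the reference.

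**4. Illustration of size.** Inputs from the documents: n = 8 recruited (section 6.0) and 4 targeted to complete (section 11.0). Assumptions: a true proportion p of participants with irritation, and a chance s that an affected participant is recorded as such.

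Chance of recording at least one case = 1 − (1 − p·s)^n.

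| p (assumed) | n | s = 1 | s = 0.75 | s = 0.50 | s = 0.25 |
|---|---|---|---|---|---|
| 0.10 | 8 | 57% | 46% | 34% | 18% |
| 0.20 | 8 | 83% | 73% | 57% | 34% |
| 0.30 | 8 | 94% | 87% | 73% | 46% |
| 0.20 | 4 | 59% | 48% | 34% | 19% |

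Example: p = 0.20, s = 0.50, n = 8 gives 1 − 0.90^8 = 0.57.

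**5. What would zero events show?** The one-sided 95% upper bound with no events and full detection is 1 − 0.05^(1/n): 31.2% for n = 8 and 52.7% for n = 4. With detection s the bound on the true proportion becomes that figure divided by s. For n = 8 it is 0.312/0.75 = 41.6% or 0.312/0.50 = 62.4%. Small n already makes a zero count weak evidence, and incomplete detection weakens it further.

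**The case against.** The strongest reply has five parts.

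- **Fingertip is not wrist.** The criterion concerns fingertips and lists alternatives, so a person could qualify on two-point discrimination or tingling. A reader might infer that these participants cannot feel irritation under the band. The documents do not support that, since they say nothing about touch, itch or pain at the wrist. This stands, and the point is limited to a possibility in some participants.
- **The wrist is visible.** Participants can report redness that they see. Staff provide the device, meet participants three times a week and may inspect the skin. This also stands: a miss is possible, not certain. It does not make inspection required or recorded.
- **Patient experience exists.** A reader might infer that the no-irritation record comes only from the investigators' own use. It does not, because section 14.0 also cites chronic stroke survivors. Neither statement gives sensory status at the wrist or says how skin was checked.
- **The risk is called minor and rare.** Section 14.0 does describe it so, and being named first in a list does not show importance. The exclusion of compromised hand or wrist skin due to long-term blood thinners lowers the risk further. This limits the consequence but does not settle the method.
- **Sample size dominates.** With 8 participants the zero-event bound is 31% even with perfect detection. That is correct, and a reason to rate the point as modest.

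A reader might also see the imperceptible vibration as a lost warning cue. It is subthreshold by design, whatever the wrist sensation, so it has no bearing here.

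**Conclusion.** The point holds in a limited form. The wording lets verbal report stand alone for a named device risk, in a population selected for fingertip touch deficits and with the band on the affected limb. No other provision requires anyone to look at the skin, and the rule for new irritation has no required baseline inspection to refer to.

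The conclusion rests on one inference that the documents do not state: that wrist sensation is reduced in at least some participants. The lack of a baseline inspection does not depend on that inference.

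The size of any under-detection cannot be estimated. A reader might take a particular share of missed events from the illustration, but p and s are assumptions and the documents favour no value of either. Nor does the point reach the primary aim, the association between connectivity change and motor gain. It is a small, inexpensive improvement to the safety data of a single-site pilot.

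**What to change.** In section 12.0, replace *and/or* with *and* in the skin irritation item. Verbal report and visual examination of the skin under the wristband and the vibrator would then both be done and recorded for every participant at baseline and at every evaluation time point. State in the adverse event criterion that new irritation is judged against the recorded baseline examination.

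The cost is about a minute per evaluation (an estimate), within the 10 minutes that section 12.0 already allots to safety assessment. At 8 evaluations and 8 participants this is 8 × 8 × 1 = 64 minutes over the whole study. It also needs an entry on the testing sheet, but no added staff or equipment. A brief look when the band comes off after each of the 18 therapy sessions is an optional extra. The point does not depend on it.
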